7 STATISTICAL METHODOLOGY

7.1 General Considerations

For continuous variables, descriptive statistics will include the number of patients (n), mean, standard deviation, median, minimum and maximum. When needed, the use of other percentiles (e.g.10%, 25%, 75% and 90%) will be mentioned in the relevant section.

Frequencies and percentages will be displayed for categorical data. Unless otherwise specified, percentages by categories will be based on the number of patients with no missing data, i.e. will add up to 100%.

All summary tables and figures will be presented by treatment arm and overall for double-blind treatment period, unless stated otherwise. For open-label phase, only selected summaries will be presented , the titles of selected tables, listings and figures for open-label phase summaries will be written out to indicate the “Open-label Phase”, refer to Appendix 3 for detailed analyses for open-label phase. All listings will be produced by site and patient id numbers in ascending order.

Disposition, demographics and other baseline characteristics as well as efficacy data will summarized based on the ITT population, unless stated otherwise. Safety analysis summary and other summaries based on SAF are presented by actual treatment received, unless stated otherwise.

All statistical comparisons will be made using two sided tests comparing double-blind enzalutamide to double-blind placebo. All null hypotheses will be of no treatment difference. All analyses will be based on IRT captured strata. Multiplicity adjustment was incorporated within the interim and final analysis of the primary endpoint according to the O’Brien-Fleming method with a Lan-DeMets alpha spending function (refer to Section 6.1.1.1). And no adjustment for multiplicity will be made for this study on the other endpoints, hence any p-values displayed for those endpoints are intended to be read descriptively.

All data processing, summarization, and analyses will be performed using SAS® Version 9.1.3 or higher. Specifications for table, figures, and data listing formats can be found in the TLF specifications for this study.

For the definition of subgroups of interest, please refer to Section 7.9.

A data analysis cut-off date for the database will be used. All data from visits or assessments done prior to the cut-off date will be reported.

7.2 Study Population

7.2.1 Disposition of Subjects

The following subject data will be presented:

- Number of patients with informed consent form (ICF), discontinued before randomization, randomized, based on patients with ICF (not presented by treatment);
- Number and percentage of patients randomized in each analysis set, patients who took study drug, patients who did not take study drug
- Number and percentage of patients by study visit, based on the SAF
- Number and percentage of subjects who discontinued from the treatment by primary reason for discontinuation
- Number and percentage of subjects who discontinued from the safety follow-up (30 day follow-up) by primary reason for discontinuation
- Number and percentage of subjects discontinued from the post-treatment follow-up by primary reason for discontinuation;
- Number and percentage of subjects who discontinued from the long term follow-up (end of study) by primary reason for discontinuation
- Number of subjects with protocol deviations
- Number of subjects per protocol version

Screen failures information, inclusion/exclusion from analysis set, treatment disposition, 30 day follow-up disposition, post-treatment follow-up disposition, and long term follow-up disposition, randomization information and dates of first and last evaluations will be listed. The protocol deviations, as well as the description of protocol deviation criteria will also be listed.

7.2.2 Protocol Deviations

Protocol deviations as defined in the study protocol (Section 8.3 Major Protocol Deviations) will be assessed for all randomized subjects.

The protocol deviation criteria will be uniquely identified in the summary table and listing. The unique identifiers will be as follows:

- PD1 - Entered into the study even though they did not satisfy entry criteria,
- PD2 - Developed withdrawal criteria during the study and was not withdrawn,
- PD3 - Received wrong treatment or incorrect dose,
- PD4 - Received excluded concomitant treatment.

Subjects deviating from a criterion more than once will be counted once for the corresponding criterion. Any subjects who have more than one protocol deviation will be counted once in the overall summary. Other deviations outside of the categories defined above will be summarized where applicable.

The number and percentage of subjects meeting any criteria will be summarized for each criterion and in total, by treatment group, as well as by study site. Inclusion and exclusion criteria will be summarized for PD1 by treatment group and overall.

A data listing will be provided by site and subject.

7.2.3 Demographic and Other Baseline Characteristics

Descriptive statistics for age and height at study entry will be presented along with frequency tabulations for age group (< 65, 65- <75 and >= 75), race, at study entry. The weight, body mass index (BMI), ECOG status, PSA, and alkaline phosphatase (ALP) at baseline will also be presented by descriptive statistics. The 10%, 25%, 75% and 90% percentiles will be provided for PSA, and ALP at baseline.

Number and percentage of subjects randomized in each site will also be summarized.

Medical history is coded in the Medical Dictionary for Regulatory Activities (MedDRA) version 23.0, and will be summarized by System Organ Class (SOC) and preferred terms, as well as by preferred terms alone, by treatment group and overall on the ITT population.

Prostate cancer history will be summarized by presenting the number and percentage of subjects for tumor and lymph node stages, Gleason scores (less than 8 versus 8 or more) at initial diagnosis, volume of disease (Low versus High), incidence and location of metastases (incl. the number of bone lesions per category: 1, 2-4, 5-9, 10-19, 20 or more, and TNC; if a range which does not fall in one of these categories is reported, it will be reported in the category that includes the lower limit of the reported range) as well as per summary category (Bone only versus Soft tissue only versus Both bone and soft tissue), and previous therapies: prior docetaxel therapy use (none, yes) and ADT prior use or orchiectomy (none, ≤3 months, >3 months; considering the ATC 4th level ‘gonadotropin releasing hormone analogues’ or Preferred WHO name ‘degarelix’). Descriptive statistics will also be used to summarize the duration of disease, which is the duration between the date of randomization and the date of initial diagnosis (expressed in months).

Prior radiation and prior procedures will also be summarized.

Non-prostate cancer related medical history including data up to the start of study drug will be coded using MedDRA. The summary table (number and percentage of subjects) will be presented alphabetically by SOC and decreasing order of frequency of preferred terms within each SOC. An additional summary table will be presented only by preferred terms in decreasing order of frequency.

The underlying conditions and malignancy risk factors will be listed.

7.2.4 Previous, Concomitant, and Post-treatment Medications or Non-medications, and New Antineoplastic Therapy

Previous, concomitant, and post-treatment medications (both PC and non-PC related for previous and concomitant, and only PC related for post-treatment) reported in the corresponding eCRFs, will be coded with World Health Organization Drug Reference List

(WHO-DD), and will be summarized separately by presenting the number and percentage of subjects by therapeutic subgroup (ATC 2nd level) and chemical subgroup (ATC 4th level) and preferred WHO name. It will be ordered alphabetically by ATC subgroup and decreasing order of frequency of preferred WHO name within each ATC class. Subjects taking the same medication multiple times will be counted once per medication and period.

Previous and concomitant non-medications reported in the corresponding eCRF will be summarized separately by presenting the number and percentage of subjects by reported name. It will be ordered alphabetically and decreasing order of frequency of reported name. Subjects having the same non-medication multiple times will be counted once per non-medication and period.

New antineoplastic prostate cancer therapy are therapies started after the last dose date of study drug, including cytotoxic and hormone therapies. They are recorded as 'antineoplastic medication' in the eCRF (either prostate cancer drug therapy eCRF page, with 'antineoplastic medication' ticked; or on the new prostate cancer drug therapy eCRF page with 'antineoplastic medication' ticked).

All (new) antineoplastic prostate cancer therapies (started on or after first dose of study drug date) will also be summarized separately on the first new antineoplastic prostate cancer after study drug ended. The summary of first new antineoplastic prostate cancer therapy will be provided for the ITT and SAF population.

All previous, concomitant and post-treatment medications or non-medications recorded in the eCRFs will be listed, as well as all new antineoplastic prostate cancer therapies.

7.3 Study Drugs

7.3.1 Exposure

The following information on drug exposure will be presented for each treatment group for the SAF:

- The duration of exposure (number of months) to study medication will be summarized using descriptive statistics, including 10%, 25%, 75% and 90% percentiles.
- Number and percentage of patients on study drug at 6 months and at year 1, 2, 3, and 4 (that is with duration of exposure superior or equal to day 182, 365, 730, 1095, and 1461).
- Number and percent of patient with dose reductions, increases or interruptions, the reasons for these, as well as the number of these per patient.
- Descriptive statistics for the total dose and the average daily dose of the drug patient was exposed to.

7.3.2 Treatment Compliance

Percent overall compliance with the dosing schedule will be examined on drug accountability data for patients in the SAF for whom, at least a kit was returned and the first and last days of treatment (or the patient still on treatment by the cut-off date) are known.

Percent overall compliance will be summarized as follows:

- Descriptive statistics will be presented by treatment group and overall.
- Percent compliance will be categorized according to the following categories:
 - less than or equal to 70%
 - greater than 70%, less than or equal to 90%
 - greater than 90%, less than or equal to 110%
 - greater than 110%
 - Unknown.

7.4 Analysis of Efficacy

Primary and secondary efficacy analysis will be conducted on the ITT population only for double-blind treatment period unless otherwise specified.

Double-blind treatment period is defined as the period subjects being randomized to receive enzalutamide or placebo in a double-blind fashion such that neither the investigator, sponsor's study management team, clinical staff, nor the subject will know which agent is being administered.

7.4.1 Analysis of Primary Endpoint(s)

The primary efficacy variable is time to PSA progression (TTTP): PSA progression is defined as a $\geq 25\%$ increase and an absolute increase of $\geq 2 \mu\text{g/L}$ (2 ng/mL) above the nadir (i.e., lowest PSA value observed post baseline or at baseline), which is confirmed by a second consecutive value at least 3 weeks later.

The primary efficacy analysis will be performed on the TTTP for the subjects in the ITT population. TTTP is defined as the time from randomization to the date of the first confirmed observation of PSA progression. For subjects who have not had confirmed PSA progression at the time of analysis, the following censoring rules will be applied.

- Subjects who have no baseline or no post-baseline PSA assessments will be censored at the date of randomization
- Subjects who have not progressed by the data cutoff date will be censored at the date of the last PSA assessment prior to the data cutoff date
- Subjects who have not progressed but died due to any cause will be censored at the date of the last PSA assessment prior to the data cutoff date
- Subjects who discontinued from the entire study prior to the data cutoff date without evidence of PSA progression will be censored at the date of the last PSA assessment
- Subjects who have had unconfirmed PSA progression by the data cutoff date will be censored at the date of the last PSA assessment without evidence of confirmed PSA progression prior to the data cutoff date

If a subject meets the criteria for more than one censoring rule, they will be censored with the earliest censoring date. The PSA progression date is the first date where progression definition is met, not confirmed.

There are 2 planned analyses (as defined in Section 6.1.1), one final analysis at the total planned 75 PSA progression events and one interim analysis at 80% of the total planned events (about 60 PSA progression events).

The effect of Enzalutamide+ADT compared to placebo+ADT will be formally tested using a stratified log-rank test at both interim analysis and final analysis at 2-sided 0.0244 and 0.0429 significance level, respectively, according to the O'Brien-Fleming boundary as implemented by Lan-DeMets alpha spending function [Lan-DeMets, 1983]. Stratification factors are the factors used at randomization, prior docetaxel use (yes versus no) and disease volume (low versus high).

The null and alternative hypotheses to be tested are as follows:

- The null hypothesis: TPP for Placebo+ADT and Enzalutamide +ADT are not different
- The alternative hypothesis: TPP for Placebo+ADT and Enzalutamide+ADT are different

The following SAS code will be used to compute the Kaplan-Meier estimates and curves, and the stratified log-rank test:

```
PROC LIFETEST DATA=INPUT  
    ATRISK  
    PLOTS=SURVIVAL(CB)  
    OUTSURV=SURVPL  
    ALPHA=0.05  
    ALPHAQT=0.05 METHOD=KM;  
    TIME AVAL*CNSR(1);  
    STRATA STRATUM1 STRATUM2/ GROUP=TREATMENT;  
    RUN;
```

where INPUT is the input dataset

AVAL is the time to the event variable,

CNSR is 0 (patients with events) or 1 (patients without event, i.e. patient censored)

STRATUM is the stratification variable (volume of disease and prior docetaxel use)

TREATMENT is the treatment variable

Kaplan-Meier methods will be used to estimate the distribution of TPP events by treatment group. The median TPP will be estimated using the corresponding 50th percentile of Kaplan-Meier estimates. A two-sided 95% confidence interval will be provided for this estimate by use of the Brookmeyer and Crowley method. A Kaplan-Meier plot by treatment group will be presented. The estimates of the event free rate on a 3-monthly basis up to 1 year and every 6 months thereafter will be summarized by treatment group, as long as at least 10 patients are at risk.

The benefit of Enzalutamide+ADT compared to placebo+ADT will be summarized by a single HR with its 95% CI based on a Cox regression model stratified for the prior docetaxel use and disease volume. The null and alternative hypotheses regarding TPP can be rephrased in terms of the HR ($\lambda_{\text{ArmA}} / \lambda_{\text{ArmB}}$), where λ_{ArmA} represents the hazard of TPP for Enzalutamide+ADT and λ_{ArmB} represents the hazard of TPP for placebo+ADT. A HR of < 1 indicates that the

TTTP is prolonged for patients randomized to Enzalutamide+ADT compared with patients randomized to placebo+ADT. The null and alternative hypotheses, respectively, can be written as follows:

$$H_0: \frac{\lambda_{ArmA}}{\lambda_{ArmB}} = 1 \quad H_1: \frac{\lambda_{ArmA}}{\lambda_{ArmB}} \neq 1$$

The estimated HR of Enzalutamide+ADT to placebo+ADT, and its 95% confidence interval will be provided.

SAS PROC PHREG will be used for the analysis with the “DISCRETE” option for tie breaker as follows:

```
PROC PHREG DATA = INPUT;  
  MODEL AVAL*CNSR(1) = TREATMENT / TIES=DISCRETE;  
  STRATA STRATUM1 STRATUM2;  
  RUN;
```

where INPUT is the input dataset

AVAL is the time to the event variable,

CNSR is 1 (patients with no events) or 0 (patients with events)

STRATUM are the stratification variables (volume of disease and prior docetaxel use)

TREATMENT is the treatment variable

If the estimate of the HR $\lambda_{ArmA} / \lambda_{ArmB} < 1$ and the results from the log-rank test lead to the rejection of H_0 in favor of H_1 , then it will be concluded that Enzalutamide+ADT prolongs TTTP compared to placebo+ADT.

The PSA results will be summarized descriptively by visit, by presenting the mean, standard deviation, minimum, maximum and median of the results and change from baseline for the subjects in the ITT population and also for the subjects in the ITT population with detectable PSA at baseline.

Sensitivity analyses

The efficacy sensitivity analyses for TTTP as defined in Section 6.1.1.2 will be conducted on the ITT population using the same analysis methods as described above.

A forest plot displaying the HR for treatment comparison and 95% confidence interval will be presented for the different TTTP sensitivity analyses. The HR will be estimated by use of Cox proportional hazards models stratified for the prior docetaxel use and disease volume and treatment as covariate, as in the primary analysis.

SAS PROC PHREG will be used for these sensitivity analyses:

```
PROC PHREG DATA = INPUT;  
  CLASS TRTP (REF=' PLACEBO+ADT' ) STRATUM1 STRATUM2;  
  MODEL AVAL*CNSR(1) = TREATMENT / TIES=DISCRETE;  
  STRATA STRATUM1 STRATUM2;  
  RUN;
```

Subgroup analyses

Subgroup analyses of TPP and rPFS will be performed to determine whether the treatment effect is concordant among subgroups. To avoid possible issue related to small number of events, subgroup analyses will not be adjusted for the stratification factors used at randomization. Subgroups are defined in Section 7.9.

A forest plot displaying the HR for treatment comparison and 95% confidence interval will be presented by subgroup. The HR will be estimated by use of Cox proportional hazards models with treatment as covariate.

SAS PROC PHREG will be used for these subgroup analyses:

```
PROC PHREG DATA = INPUT;  
  MODEL AVAL*CNSR(1) = TREATMENT / TIES=DISCRETE;  
  BY SUBGROUP;  
  RUN;
```

7.4.2 Analysis of Secondary Endpoints

7.4.2.1 rPFS

Time to Radiographic progression-free survival (rPFS) will be analyzed using the same analysis methods as for primary analysis of TPP.

7.4.2.2 Time to First SSE

Time to first SSE will be analyzed using the same analysis methods as for primary analysis of TPP.

7.4.2.3 Time to Castration Resistance

Time to first castration resistance will be analyzed using the same analysis methods as for primary analysis of TPP.

7.4.2.4 PSA Response $\geq 50\%$, PSA Response $\geq 90\%$

The serum PSA response rate $\geq 50\%$ and $\geq 90\%$ at any time and at each visit for subjects with detectable PSA at baseline and at least 1 post-baseline assessment will be summarized. The largest decrease from baseline in PSA will be additionally presented by treatment group using a waterfall plot. PSA response $\geq 50\%$ and $\geq 90\%$ will be calculated by treatment group on the entire ITT population who have detectable PSA at baseline and at least 1 post-baseline assessment.

In patients of the ITT population with detectable PSA at baseline and at least 1 post-baseline assessment, the PSA Response $\geq 50\%$, and PSA Response $\geq 90\%$ in enzalutamide+ADT and placebo+ADT will be compared by use of the stratified Cochran-Mantel-Haenszel score test.

The SAS code used to implement the Cochran-Mantel-Haenszel score test will be:

```
PROC FREQ DATA=INPUT;  
  TABLES STRATUM*TREATMENT*RESPONSE / CMH;  
  RUN;
```

where INPUT is the input dataset

RESPONSE is the analysis variable with the $PSA \geq 50\%$ or $PSA \geq 90\%$,

STRATUM is the stratification variables (volume of disease and previous docetaxel use)

TREATMENT is the treatment variable

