#### 7.2.1 Intent-to-Treat Population

The Intent-to-Treat (ITT) population is defined as all subjects who were randomized in this

study. The ITT population will be analyzed by treatment arm as randomized (i.e., treatment arm based on randomization assignment). The ITT population will be used to conduct efficacy analyses. For the ORR, only subjects with measurable disease at baseline will be included in the analysis.

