#### PSA Response $\geq$ 50%, PSA Response $\geq$ 90%:

PSA response  $\geq$  50% is defined as  $\geq$  50% reductions in PSA level from baseline to the lowest post-baseline PSA result as determined by the central laboratory, with a consecutive assessment conducted at least 3 weeks later to confirm the PSA response. The same logic for PSA response  $\geq$  90%. The serum PSA response rate will be summarized at each time point. Waterfall plots of the rate of change from baseline will be constructed. PSA response  $\geq$  50% and  $\geq$  90% will be calculated by treatment group for subjects with PSA values at the baseline assessment and at least 1 post-baseline assessment.

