5.1 Intent-to-Treat Population

The Intent-to-Treat (ITT) population is defined as all subjects who were randomized in this study. The ITT population will be analyzed by treatment arm as randomized (i.e., treatment arm based on randomization assignment). The ITT population will be used to conduct efficacy analyses, unless otherwise specified. For the ORR, only ITT subjects with measurable disease at baseline will be included in the analysis.

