6.1.2.6 PSA Undetectable Level

The undetectable level of PSA is defined as a level $< 0.2 \text{ ng/mL}$.

For patients with a detectable level of PSA at baseline, a dichotomous variable (‘Y’/‘N’) is derived to assign ‘Y’ to patients with any post-baseline PSA sample results $< 0.2 \text{ ng/mL}$. otherwise ‘N’ is assigned. For patients with undetectable level of PSA at baseline, this variable is kept missing.

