7.12 Handling of Missing Data, Outliers, Visit Windows, and Other Information

The baseline measurement is the last measurement taken prior to initial study drug administration. Both date and time of drug administration and measurement should be considered to identify the baseline value. If the time is not available, then date only will be used and it will be considered that assessments on day 1 are done pre-dose.

Change from baseline is defined as (post baseline value - baseline value).

To calculate time interval duration, a month is 30.4375 days and a year 365.25 days. Duration expressed in years or months are rounded up to 1 significant digit. The duration between 2 dates d1 and d2 is (d2-d1+1) in days (with d1 before d2).

Treatment day and study day will be calculated in reference to the date of the first dose of study drug. Treatment Day 1 corresponds to the date the patient received the first dose of study drug. For assessments conducted on or after the date of the first dose of study drug, treatment day will be calculated as (assessment date - date of first dose of study drug) + 1. There will be no Treatment Day 0.

Unless otherwise specified, the date of study drug discontinuation refers to the study drug last dose date. Should that date be partially missing, the end of treatment date recorded on the end of treatment form will be used.

Time to event endpoints will be based on the actual date of event rather than visit date. The date of randomization will always be considered as the start date for the time interval.

For laboratory results collected as < or > a numeric value, 0.0000000001 will be subtracted or added, respectively, to the value unless otherwise specified.

Percentages will be calculated based on the number of patients with non-missing data as the denominator unless otherwise specified.

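### PSA response rates (≥50% and ≥90%) are compared only in patients with a post-baseline PSA, while the PSA undetectable rate and ORR keep unassessed patients as non-responders

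*SAP*

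**What the plan says.** **PSA response.** SAP 7.4.2.4 gives the rates "on the entire ITT population who have detectable PSA at baseline and at least 1 post-baseline assessment" and sets the same population for the treatment comparison: "In patients of the ITT population with detectable PSA at baseline and at least 1 post-baseline assessment". SAP 6.1.2.4 carries the condition into the endpoint definition and admits only samples taken before any new antineoplastic therapy. Protocol 7.4.2 already had the post-baseline condition: the rates "will be calculated by treatment group for subjects with PSA values at the baseline assessment and at least 1 post-baseline assessment". The protocol synopsis repeats it. The baseline half differs slightly (a PSA value in the protocol, a detectable PSA in the SAP), but that is fixed before treatment and is not at issue here.

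**General rules.** SAP 5.1: "The ITT population will be used to conduct efficacy analyses, unless otherwise specified". SAP 7.12: "Percentages will be calculated based on the number of patients with non-missing data as the denominator unless otherwise specified". Protocol 7.2.1: "The ITT population will be used to conduct efficacy analyses". The protocol sentence has no exception clause, and the section names only ORR as restricted to a subset.

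**The other binary endpoints.** SAP 6.1.2.6 codes Y for "patients with any post-baseline PSA sample results" below 0.2 ng/mL and N otherwise. SAP 7.4.2.6 compares the undetectable rate in all ITT patients with detectable baseline PSA. For ORR, SAP 7.4.2.7 uses all ITT patients with measurable baseline disease, and SAP 6.1.2.7 places those with no post-baseline assessment in a not-evaluated category, which is neither CR nor PR.

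**The concern.** The requirement for a post-baseline PSA is met or failed after randomisation. A patient who dies, withdraws or is lost before giving a sample leaves both the numerator and the denominator, so the groups being compared are no longer quite the randomised ones.

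Three PSA rates built from the same central-laboratory samples will therefore appear in one report on two denominators. The wording of SAP 7.4.2.4 also speaks of the entire ITT population before narrowing it, so a reader could take the result for an ITT estimate. What is at stake is the comparability and interpretation of two secondary endpoints.

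**Working it through.** **Inputs.** Planned arms are 120 and 60 (Protocol 7.1; SAP 4). The documents give no expected PSA response rate and no expected number without post-baseline PSA, so there is no plan figure to reproduce on this point. Assumptions: every randomised patient has detectable baseline PSA, and observed rates lie between 50% and 90%. If fewer patients have detectable baseline PSA, n falls and each excluded patient counts for more.

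**Direction.** Let n be the patients in an arm with detectable baseline PSA, m those of them with no eligible post-baseline PSA, and r the responders.
- Rate as planned: p = r/(n − m).
- Rate counting the m as non-responders: r/n = p × (n − m)/n.
- Overstatement: p − p × (n − m)/n = p × m/n, which is positive whenever m > 0 and r > 0.

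**One patient (m = 1).**
- n = 120: 0.90/120 = 0.75 points; 0.50/120 = 0.4 points.
- n = 60: 0.90/60 = 1.5 points; 0.50/60 = 0.8 points.

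**Larger shares.**
- 5% of an arm (6 of 120 or 3 of 60): 0.05 × 0.50 = 2.5 points to 0.05 × 0.90 = 4.5 points.
- 10% of an arm (12 of 120 or 6 of 60): 5 to 9 points. The 10% is the dropout figure from the sample-size section, used only as a ceiling. It is not an estimate of missing post-baseline PSA.

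**Treatment difference.** Take assumed observed rates of 90% and 70%, a difference of 20.0 points.

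| No post-baseline PSA (enzalutamide / placebo) | Enzalutamide | Placebo | Difference |
|---|---|---|---|
| 2 / 1 | 0.90 × 118/120 = 88.5% | 0.70 × 59/60 = 68.8% | 19.7 |
| 12 / 6 | 0.90 × 108/120 = 81.0% | 0.70 × 54/60 = 63.0% | 18.0 |
| 2 / 6 | 88.5% | 63.0% | 25.5 |
| 12 / 0 | 81.0% | 70.0% | 11.0 |

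Each arm's rate falls, but the difference can shrink or grow. Only the first row is close to what the visit schedule makes plausible; the others bound the effect.

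**How many patients could be affected.** The first post-baseline PSA is due at day 29 (Protocol Table 1). Stopping study drug does not end collection: PSA is also drawn at the safety follow-up visit (Protocol 5.3.1.1), which falls 30 days after the last dose or before new therapy, whichever is first. Patients who stop without confirmed radiographic progression then have PSA every 12 weeks. Those left are mainly patients who die, withdraw consent, are lost or miss samples before any post-baseline draw. Entry requires ECOG 0 or 1 and a life expectancy of at least 12 months, so this group should be small.

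**The case against.** **A reader might infer that the plan breaks its own ITT rule.** The documents do not support that for the SAP. Section 5.1 allows specified exceptions, 7.4.2.4 specifies one, 7.12 makes non-missing denominators the default, and the protocol set the same post-baseline condition in its synopsis and in 7.4.2. All that remains is a loose fit inside the protocol: 7.2.1 names ORR as the only subset, while 7.4.2 restricts PSA response "for subjects with PSA values at the baseline assessment and at least 1 post-baseline assessment".

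**A reader might also infer that patients stopping early for toxicity are removed, to enzalutamide's advantage.** The schedule answers most of this. Such a patient should still give a PSA at the safety follow-up visit, before any new therapy starts. No direction of bias in the treatment difference is shown, as the table makes plain.

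**The strongest remaining defence is that this is a disclosed convention with little consequence.** SAP 7.1 makes no multiplicity adjustment for secondary endpoints and reads their p-values descriptively. The primary analysis keeps patients without post-baseline PSA in the ITT set, censored at randomisation. The undetectable rate has its own stated definition, so the two rules do not contradict each other. All of that stands, and it limits the importance of the point. It does not justify the choice: disclosure makes the restriction transparent but does not restore the randomised comparison, and the plan does not say why one PSA rate counts these patients and two do not.

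**Conclusion.** The point holds as a minor, inexpensive improvement. Both PSA response rates and their test are conditioned on post-randomisation data. Each arm's rate is overstated by p × m/n relative to non-responder counting, and the rule is inconsistent with the PSA undetectable rate and ORR. It is a pre-specified exception, not a departure from the SAP's ITT rule.

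At an assumed 90% observed rate the size is 0.75 points per excluded patient in the 120-patient arm and 1.5 points in the 60-patient arm, if all randomised patients have detectable baseline PSA. The actual number excluded is unknown and probably small. The effect on the treatment difference has no fixed sign. The primary endpoint and its type I error are unaffected.

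**What to change.** In SAP 6.1.2.4 and 7.4.2.4, define the denominator for the overall (any-time) response rates and for the Cochran-Mantel-Haenszel test as all ITT patients with detectable baseline PSA. State that patients with no post-baseline PSA before new antineoplastic therapy count as non-responders. This must be explicit, because the default in SAP 7.12 would otherwise take them out again. Keep the present denominator as a supportive analysis, and report by arm the number without post-baseline PSA. By-visit summaries and the waterfall plot can stay on observed values.

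Add a matching note to the protocol synopsis and Protocol 7.4.2. While editing, settle whether a response needs confirmation at least 3 weeks later: the protocol requires it, and the SAP definition does not mention it. The non-responder rule above does not depend on the answer.

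**Cost.** Short edits at each place where the condition appears, and no new data. SAP 1 allows revision before database hard lock. The stated response rates may be slightly lower.
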